4.4.4 Handling of Missing Values/Censoring/Discontinuations

Missing data will not be replaced or imputed. Subjects who withdraw from the study prematurely will be included in the statistical analyses up to the point of discontinuation.

The use of MMRM analyses account for missing data assuming a missing at random assumption, i.e., there is a systematic relationship between the propensity of missing values and the observed data, but not the missing data.

It is therefore assumed that a subject with missing data would have obtained a similar efficacy result compared to a subject using the same study product with the same smoking status and similar non-missing results at other timepoints (baseline and post-baseline). Sensitivity analyses may be added to the SAP prior to unblinding in case of high drop-out rates and/or exclusion from PP analyses.

4.5 Analysis of Safety

The safety profile of the study treatments will be assessed with respect to AEs or incidents or others such as OST/OHT abnormalities in oral health study.

4.5.1 Adverse Events and Serious Adverse Events

All AEs will be reviewed by the Clinical Research Scientist or Designee prior to database lock and will be coded to a system organ class (SOC) and preferred term (PT) using the Medical Dictionary for Regulatory Activities (MedDRA).

AEs will be classified as oral and non-oral on the AE page of eCRF.

Treatment emergent adverse events (TEAEs) are defined as new AEs that occur on or after the first study product use (if this date is missing a suitable alternative will be used e.g., date of randomization). AEs with an onset date/time prior to the first study product use will be considered as non-treatment emergent.

The following summary tables and listings will be presented by study product group.

- Table of TEAEs by SOC and PT (Table 14.3.1.1).
- Table of TEAEs by Oral/Non-Oral and PT (Table 14.3.1.2)
- Table of treatment related TEAEs by SOC and PT (Table 14.3.1.3)
- Table of treatment related TEAEs by Oral/Non-Oral and PT (Table 14.3.1.4)
- Table of AEs related to COVID-19 by SOC and PT (Table 14.3.1.5).
- Listing of all AEs (Listing 16.2.7.1 for all randomized subjects; Listing 16.2.7.2 for non-randomized subjects)
- Listing of deaths (Listing 14.3.2.1)
- Listing of non-fatal SAEs (Listing 14.3.2.2)
- Listing of TEAEs leading to study or drug withdrawal (Listing 14.3.2.3)
- Listing of TEAEs classified as Oral (Listing 14.3.2.4)
- Listing of all AEs related to COVID-19 (Listing 16.2.7.3 for all screened subjects)

In the event that there is nothing to report, a null table or listing will be produced.

All Incidents will be listed in Listing 16.2.7.4. In the event that there is nothing to report, a null listing will be produced.

4.5.2 Other Safety Variables

Other safety variables are listed below:

- OST examination
- OHT examination

4.5.2.1 OST Examination

This procedure will be conducted by a qualified, experienced clinical examiner. The OST examination will be accomplished by direct observation and palpation with retraction aids, as appropriate. The examination will cover the oral labial mucosa (including lips), buccal mucosa, mucogingival folds, gingival mucosa, hard palate, soft palate, tonsillar area, pharyngeal area,

tongue, sublingual area, submandibular area, and salivary glands. Findings from the examination will be recorded in the CRF as either normal or abnormal, with details of any abnormalities. The results of the OST examination performed at screening will be used to determine subject eligibility. Any new OST abnormality or worsening of a pre-existing condition observed by the clinical examiner or reported by the subject after the screening examination will be recorded as an AE. Where possible, this procedure should be conducted by a single clinical examiner.

OST will be summarized (number of subjects and percentages with abnormalities, without abnormalities, or OST not examined) by visit and study product in Table 14.3.4.1 for all subjects in Safety Population. OST examination will be listed (Listing 16.2.8.1) for all randomized subjects.

4.5.2.2 OHT Examination

This procedure should be conducted by a qualified, experienced clinical examiner. The OHT examination will be accomplished by direct observation, using retraction aids as appropriate and will identify any grossly carious lesions, signs of erosive wear, enamel irregularities, tooth fracture, gross generalized dental caries decay, decalcification, and faulty restorations. The presence of any implants, fixed or removable dentures, fixed or removable orthodontic braces/bands, fixed orthodontic retainers, full crowns or veneers will be recorded. Observations will be listed as either absent or present, and conditions noted as present will be described in the eCRF. Any change observed by the clinical examiner or reported by the subject after the screening examination will be recorded as an AE. The results of the OHT examination performed at Screening will be used to determine subject eligibility. Where possible, this procedure should be conducted by a single clinical examiner.

OHT examination will be listed (Listing 16.2.8.2) for all randomized subjects.

4.6 Analysis of Other Variables

Repeat individual MLSI and tooth shade assessments will be performed by the clinical examiner at Baseline-Day 0 (Visit 2), Week 4 (Visit 3), and Week 8 (Visit 4). To assess the repeatability of the MLSI and tooth shade assessments, replicate examinations will be performed by the same clinical examiner.

Ten subjects will be randomly selected for repeat MLSI and tooth shade assessments at each assessment time point (Visits 2, 3, and 4), a total of 30 repeat assessments (for both MLSI and tooth shade assessments) over the duration of the study. Replicate assessments will be separated by a minimum of 10 minutes (maximum 60 minutes) from the original assessment for a given subject and, where possible, separated by at least one subject.

The scores of the initial assessment will not be visible to the examiner or scribe when the repeat assessment is carried out.

The repeat dental assessments (MLSI and tooth shade assessments) will be compared to the respective original assessments and will be used to investigate intra-examiner variability. The repeat assessments will not be used in any efficacy analyses.

The first and repeat assessments for each tooth site will be cross tabulated for MLSI (by Area and Intensity) (Table 14.2.7.1) and for tooth shade assessments (Table 14.2.7.2).

A weighted Kappa coefficient (κ), along with the 95% CIs will be calculated to assess the intra-examiner repeatability across all initial versus repeat assessments performed. Fleiss-Cohen weighted kappa using the raw scores will be calculated for the repeatability analysis. Repeatability will be deemed:

- Excellent if $\kappa > 0.75$
- Fair to good if $0.4 \leq \kappa \leq 0.75$
- Poor if $\kappa < 0.4$

This analysis will be conducted for MLSI using the MLSI Repeatability population and for tooth shade assessments using the VITA Shade Repeatability population. Only results with non-missing initial and repeat assessments of the same value (MLSI area, MLSI intensity or tooth shade) at the same tooth site/surface will be presented and analyzed.

5 Changes to the Protocol Defined Statistical Analysis Plan

There were below changes to the originally planned statistical analysis specified from the protocol version 3.0 (Dated: 07-SEP-2022).

Initially it was planned for primary analysis of Mean Total MLSI ($A \times I$) to provide adjusted mean difference between study product groups, adjusted 95% CIs and adjusted p-values (following graphical testing approach) in Table 14.2.2.2.1. However, adjusted 95% CIs will no longer be provided in the table. In place of adjusted CIs, we will provide standard 95% CIs.

Similarly in secondary endpoint 1 (Mean VITA shade score) related Table 14.2.3.2.1, we will provide standard CIs in place of adjusted CIs.

For secondary and exploratory endpoints not related to MLSI, an additional fixed effect for the Total MLSI ($A \times I$) strata (< 45 or ≥ 45) will be included in the MMRMs.

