5.2 Inclusion Criteria

An individual must meet all the following inclusion criteria to be eligible to be included into the study:

1. Provision of a signed and dated informed consent document indicating that the subject has been informed of all pertinent aspects of the study before any assessment is performed.
2. Subject is of either sex and any gender who, at the time of screening, is between the ages of 18-65 years, inclusive.
3. Subject who is willing and able to comply with scheduled visits, product usage requirements, study procedures and lifestyle restrictions.
4. Subject in good general and mental health with, in the opinion of the investigator or medically qualified designee, no clinically significant or relevant abnormalities in medical history (for example, a medical condition confirmed to be causing xerostomia), or upon oral examination, that would impact the subject's safety, wellbeing or the outcomes of the study, if they were to participate in the study, or affect the subject's ability to understand and follow study procedures and requirements.
5. Subject with generally good oral health with:
 - a. At least 16 natural (vital) teeth including 11 of the 12 anterior teeth.

- b. Facial surfaces of all anterior teeth (maxillary and mandibular) and lingual surfaces of anterior teeth (mandibular only) gradable for MLSI with no significant calculus or large restorations as judged by the clinical examiner.
- c. Presence of extrinsic dental stain (formed on the surface of the teeth) which, in the opinion of the clinical examiner, originates from the diet and/or use of tobacco products.
- d. Facial surfaces of central and lateral maxillary incisors gradable for tooth shade (free of cervical margin defects and restorations which could impact assessment), as judged by the clinical examiner.
- e. Baseline Total MLSI $(A \times I) \geq 15$ for the facial surfaces of the 12 anterior teeth.
- f. Baseline mean tooth shade (VITA Bleachedguide 3D-MASTER) ≥ 11 on the facial surfaces of the 4 maxillary incisors.

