9.2.1.1 Repeatability of the MLSI Assessment

To assess the repeatability of the MLSI assessments, replicate examinations will be performed by the same clinical examiner. Ten subjects will be randomly selected for repeat MLSI assessments at each assessment time point (Visits 2, 3 and 4), a total of 30 repeat assessments over the duration of the study. Replicate assessments will be separated by a minimum of 10 minutes (maximum 60 minutes) from the original assessment for a given subject and, where possible, separated by at least one subject.

The scores of the initial assessment will not be visible to the examiner or scribe when the repeat assessment is carried out.

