12.3.4 Other Analyses

The repeat stain and color assessments will be compared to the original assessments and will not be used in any efficacy analysis. The first and second assessments on each tooth site will be cross tabulated. A weighted Kappa coefficient (κ), along with the 95% CI will be calculated

to assess the intra-examiner reliability. Fleiss-Cohen weighted kappa will be calculated for the repeatability analysis. Reliability will be deemed

- Excellent if $\kappa > 0.75$
- Fair to good if $0.4 \leq \kappa \leq 0.75$
- Poor if $\kappa < 0.4$

All subjects who have repeatability data will be included in this analysis.

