4.4.2 Secondary Efficacy Endpoints

4.4.2.1 Secondary Efficacy Endpoint 1

The Secondary Efficacy Endpoint 1 will be the change from baseline in the mean VITA shade score at week 8 within each study product.

Tooth shade (color) of the facial surfaces of the four central and lateral maxillary incisors (tooth numbers 7-10) will be assessed by a single, trained clinical examiner using the VITA Bleachedguide 3D-MASTER. The VITA Bleachedguide 3D-MASTER uses a value-ranked

ordered scale from 1 (the lightest) to 29 (the darkest). The shade level of each tooth surface is scored visually by the clinical examiner with reference to the Bleachedguide.

The mean VITA shade score for each subject at each visit is calculated as the mean VITA shade score over all non-missing facial surfaces of the four central and lateral maxillary incisors.

Descriptive statistics (n, mean, SD, Standard Error [SE], median, minimum, and maximum) will be presented for the mean VITA shade score at each assessment time point (absolute and change from baseline) in Table 14.2.3.1.1 for all subjects in mITT Population by study product. Raw means (\pm SE) of mean VITA shade scores at each time point will be plotted by study product in Figure 14.2.2.1 respectively for all subjects in mITT population.

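### The 95% CI for the pooled MLSI repeatability kappa (SAP 4.6) makes no allowance for clustering of tooth sites within a subject (minor; one sentence to fix)

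*SAP*

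**What the plan says.** Both documents make the tooth site the unit of the repeatability table. Protocol 12.3.4: "The first and second assessments on each tooth site will be cross tabulated". SAP 4.6: "The first and repeat assessments for each tooth site will be cross tabulated for MLSI", separately for Area and Intensity. The SAP then limits the analysis to complete pairs: "Only results with non-missing initial and repeat assessments of the same value (MLSI area, MLSI intensity or tooth shade) at the same tooth site/surface". One Fleiss-Cohen weighted kappa on the raw scores is calculated for each measure, "along with the 95% CIs will be calculated to assess the intra-examiner repeatability across all initial versus repeat assessments performed".

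The pairs come from few examinations. Protocol 9.2.1.1: "Ten subjects will be randomly selected for repeat MLSI assessments at each assessment time point" (Visits 2, 3 and 4), 30 in all. Neither document says that the ten subjects must differ from visit to visit.

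No variance estimator or CI method for kappa is named in SAP 4.6 or Protocol 12.3.4. SAP section 4 gives the software only as SAS 9.4 or higher, and the changes listed in SAP section 5 do not mention kappa. SAP 4.6 also limits what depends on this analysis: "The repeat assessments will not be used in any efficacy analyses".

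**The concern.** Sites in one mouth share diet, smoking and oral hygiene. Sites read in one sitting also share the examiner's state and the viewing conditions. The plan itself expects subjects to differ in stain level, since it stratifies randomization on the whole-mouth score and on smoking. Thousands of site pairs from 30 examinations are therefore unlikely to carry the information of as many independent pairs.

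The standard large-sample CI for a weighted kappa, computed from the pooled cross-tabulation, has no cluster term. If that interval is what gets programmed, the report may claim to know the repeatability of the single examiner's MLSI scoring more precisely than it does. MLSI is the instrument behind the primary endpoint, and the SAP has chosen to report this interval as its measure of precision.

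**Working it through.** **Counts from the documents**

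- Examinations: 10 subjects x 3 visits = 30, which agrees with the stated total.
- MLSI surfaces per examination: 12 facial + 6 lingual = 18. At 4 sites each: 18 x 4 = 72 pairs.
- MLSI pairs in total: 30 x 72 = 2,160 for Area and the same for Intensity.
- 72 is a maximum, because Protocol 5.2 requires "At least 16 natural (vital) teeth including 11 of the 12 anterior teeth". One missing mandibular tooth removes a facial and a lingual surface: 72 - 2 x 4 = 64, and 30 x 64 = 1,920.
- Tooth shade is scored "over all non-missing facial surfaces of the four central and lateral maxillary incisors" (SAP 4.4.2.1): 4 x 30 = 120 pairs.

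**Model (all parameters assumed)**

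The documents give no within-examination correlation, so a range was simulated.

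- Latent stain = sqrt(rho) x subject effect + sqrt(1 - rho) x site effect, with variance 1.
- Each reading adds error with SD 0.5. Either 0% or 20% of that error variance is shared by all sites in an examination.
- Readings are cut at 0, 0.7 and 1.4 to give scores 0-3.
- Each run has 30 distinct subjects with 72 sites; there are 2,000 runs per setting.
- True kappa is about 0.71. The independent-pair 95% half-width is 0.024.

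The SE ratio is the empirical SD of kappa divided by the mean independent-pair SE. Coverage is that of kappa +/- 1.96 x the independent-pair SE.

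| Latent correlation | No shared error: SE ratio (coverage) | 20% shared error: SE ratio (coverage) |
|---|---|---|
| 0-0.06 | 1.0 (94-95%) | 1.3-1.4 (84-86%) |
| 0.10-0.15 | 1.1 (92-93%) | 1.4-1.5 (80-85%) |
| 0.24 | 1.4 (85%) | 1.7 (75-77%) |

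For latent correlations of 0-0.24 the half-width should be 0.024-0.042 instead of 0.024. The shortfall is at most 0.042 - 0.024 = 0.018, about 0.02.

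**Variations**

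- 64 sites per examination: SE ratio 1.0-1.6, coverage 80-96%.
- 36 further settings (correlation 0.03, 0.15 or 0.24, 0% or 20% shared error, varying error SD and proportion of unstained sites; kappa 0.54-0.81): SE ratio 0.94-1.71, coverage 75-96%.
- Latent correlation 0.5, as an outer case: SE ratio 2.2-2.4, coverage 57-63%.
- A separate model with kappa about 0.65, up to 50% of stain variance between subjects and up to 30% shared error: SE ratio up to 2.8, coverage down to 52%.
- Tooth shade, correlation 0-0.24: SE ratio 1.0-1.13, coverage 92-94%, half-width 0.066-0.074 instead of 0.066.

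**Where 0.24 comes from**

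Table 1-4 of the SAP assumes an SD of 0.4 for the 8-week change in mean Total MLSI. If the per-site change SD is S, then rho = (0.16 x 72/S^2 - 1)/71. S = 0.8 gives (18 - 1)/71 = 0.24; S = 1 gives 10.52/71 = 0.15; S = 0.6 gives (32 - 1)/71 = 0.44. No document gives S. The formula also concerns changes in Area x Intensity, not same-day Area or Intensity scores. It served only to choose a range. The correlations in the table are latent: without shared error, 0.24 corresponds to about 0.15 between observed scores, and 0.15 to about 0.10.

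**A CI with the subject as cluster**

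The interval kappa +/- t(n-1) x the delete-one-subject jackknife SE covered 94-96% in the main MLSI runs, 93-94% at correlation 0.5, 93-97% in the 36 further settings and 94-95% for shade.

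**The case against.** The strongest reply is that this is an unspecified detail and not an error. No sentence in either document says that sites will be treated as independent, and the output templates for Tables 14.2.7.1 and 14.2.7.2 are not in the text available. A reader might infer that the SAP prescribes an invalid interval. It does not; it leaves the method open. That stands. But the SAP does prescribe a pooled site-level table, and the default interval from such a table assumes independence, so silence leaves a poor choice likely.

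The second reply is that nothing depends on the interval. The bands apply to kappa itself, repeatability is not a study objective or endpoint, and neither table is marked for topline reporting. An error of about 0.02 is also small beside a middle band 0.75 - 0.40 = 0.35 wide. That stands too, and it keeps the point minor.

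The third reply is that the size is set by assumption and the range includes no effect at all. This is correct. The figures show what could happen and do not estimate what will.

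In the other direction, a reader might apply the usual design effect, 1 + (72 - 1) x ICC. At ICC 0.10 it is 8.10, so an interval sqrt(8.10) = 2.85 times wider; at 0.30 it is 22.3, or 4.72 times wider. That formula is for a mean. Kappa compares two readings of the same site, so a shared stain level does not act on it in the same way. At an observed correlation of about 0.10 (latent 0.15, no shared error) the simulated ratio is about 1.1.

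**Conclusion.** The gap is real and minor. The plan requests a 95% CI on a kappa pooled over up to 2,160 site pairs from 30 examinations and makes no allowance for clustering within a subject. If the ordinary interval is used, it will be too narrow to the extent that scores or reading errors correlate within an examination. For latent correlations of 0-0.24 in the assumed model, the SE is understated by a factor of 1.0 to about 1.7. Stronger clustering would make it worse, and the documents supply no upper limit.

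Two wider conclusions may tempt a reader. One is that the examiner's reliability rating, or the primary endpoint that rests on the same instrument, is in doubt. The documents do not support this: the label is read from the kappa estimate, and the repeat scores stay out of every efficacy analysis. The other is that Table 1-4 fixes the correlation. It does not, since its SD concerns 8-week changes and no per-site SD is given. Tooth shade shares the omission, but with four surfaces per examination the effect is small.

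**What to change.** Keep the Fleiss-Cohen estimate and the bands, and add to SAP 4.6 a sentence such as:

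*The 95% CI for each weighted kappa (MLSI Area, MLSI Intensity, tooth shade) will be kappa +/- t(n-1) x the delete-one-subject jackknife SE, removing all sites and visits of a subject together, where n is the number of subjects in the respective repeatability population; the upper limit will be capped at 1.*

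Deleting whole subjects also covers anyone drawn at more than one visit, although the simulations used 30 distinct subjects and did not test that case. The cap is needed because a symmetric interval can pass 1 when agreement is near perfect.

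A subject-level cluster bootstrap is an acceptable alternative. In the separate model above, a percentile bootstrap of whole examinations covered 87-93%, so the jackknife with t(n-1) is the better first choice at about 30 clusters.

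The cost is a few lines of code and a wider interval. With about 30 clusters, coverage may still fall slightly below 95%. If clustering turns out to be negligible, little is gained and little is lost.

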Appendix 1: List of Data Displays

CSR Section	TLF	Number	Title	Population	Template	Topline
14.1 Demographic Data Summary Tables and Figures						
	Table	14.1.1	Subject Disposition	All Screened Subjects	14.1.1	Yes
	Table	14.1.2	Incidence of Important protocol deviations	All randomized subjects	14.1.2	
	Table	14.1.3.1	Demographic and Baseline Characteristics	miITT Population	14.1.3.1	Yes
	Table	14.1.3.2	Demographic and Baseline Characteristics	Safety Population	14.1.3.1	
14.2 Efficacy Data Summary Tables and Figures						
	Table	14.2.1	Summary of Brushing Compliance	miITT Population	14.2.1	
	Table	14.2.2.1.1	Summary of Mean Total MLSI (A×I) Score	miITT Population	14.2.2.1.1	Yes
	Table	14.2.2.1.2	Summary of Mean Total MLSI (A×I) Score	PP Population	14.2.2.1.1	
	Table	14.2.2.2.1	Statistical Analysis of Change from Baseline in Mean Total MLSI (A×I) Score	miITT Population	14.2.2.2.1	Yes
	Table	14.2.2.2.2	Statistical Analysis of Change from Baseline in Mean Total MLSI (A×I) Score	PP Population	14.2.2.2.1	
	Table	14.2.3.1.1	Summary of Mean VITA Shade Score	miITT Population	14.2.3.1.1	Yes
	Table	14.2.3.1.2	Summary of Mean VITA Shade Score	PP Population	14.2.3.1.1	
	Table	14.2.3.2.1	Statistical Analysis of Change from Baseline in Mean VITA shade score	miITT Population	14.2.3.2.1	Yes

CSR Section	TLF	Number	Title	Population	Template	Topline
	Table	14.2.3.2.2	Statistical Analysis of Change from Baseline in Mean VITA shade score	PP Population	14.2.3.2.1	
	Table	14.2.4.1	Summary of Mean MLSI (A*I) Score by Sites (Interproximal/Gingival/Body)	miITT Population	14.2.4.1	
	Table	14.2.4.2	Statistical Analysis of Change from Baseline in Mean MLSI (A*I) Score by Sites (Interproximal/Gingival/Body)	miITT Population	14.2.4.2	
	Table	14.2.5.1	Summary of Mean MLSI Score by Area and Intensity	miITT Population	14.2.5.1	
	Table	14.2.5.2	Statistical Analysis of Change from Baseline in Mean MLSI Score by Area and Intensity	miITT Population	14.2.5.2	
	Table	14.2.6.1	Summary of Mean VITA EasyShade color co-ordinates (L*, a*, b*, WI _D and Delta E*) score	miITT Population	14.2.6.1	Yes
	Table	14.2.6.2	Statistical Analysis of Change from Baseline in Mean VITA EasyShade color co-ordinates (L*, a*, b*, WI _D and Delta E*) score	miITT Population	14.2.6.2	Yes
	Table	14.2.7.1	Intra-examiner Repeatability Analysis of MLSI Score	MLSI Repeatability Population	14.2.7.1	
	Table	14.2.7.2	Intra-examiner Repeatability Analysis of VITA Shade Score	Vita Shade Repeatability Population	14.2.7.2	
	Figure	14.2.1.1	Mean Total MLSI (A*I) Score Mean (\pm SE) Plot Over Time by Product Group	miITT Population	14.2.1.1	
	Figure	14.2.1.2	Mean Total MLSI (A*I) Score Mean (\pm SE) Plot Over Time by Product Group	PP Population	14.2.1.1	

CSR Section	TLF	Number	Title	Population	Template	Topline
	Figure	14.2.2.1	Mean VITA Shade Score Mean (\pm SE) Plot Over Time by Product Group	mITT Population	14.2.2.1	
	Figure	14.2.2.2	Mean VITA Shade Score Mean (\pm SE) Plot Over Time by Product Group	PP Population	14.2.2.1	
	Figure	14.2.3	Mean VITA EasyShade color co-ordinates (L*, a*, b*, WI _D and Delta E*) Score Mean (\pm SE) Plot Over Time by Product Group	mITT Population	14.2.3.1	
